1.4 Relevant Literature and Data

There is a growing literature on the use of tACS to understand the role of brain oscillations in behavior, cognition, and memory (see references Negahbani). Brain stimulation by constant electric currents applied to the scalp (tDCs) modulates neuronal excitability in humans (Wagner, Valero-Cabre et al. 2007; Zaghi, Acar et al. 2010; Stagg and Nitsche 2011). Transcranial current stimulation with sine-wave stimulation waveforms (transcranial alternating current stimulation, tACS) likely enhances cortical oscillations in a frequency specific manner. The mechanisms of weak electric fields generated by tDCS and tACS previously have been demonstrated to interact with cortical network activity by altering the temporal activity structure of electric signaling in cortex ([name] and McCormick 2010; Ali, Sellers et al. 2013).

The rationale for this stimulation is the known deficits in the overall structure of cortical activity in this frequency band in patients with mood disorders (Henriques and Davidson 1990; Baehr, Rosenfeld et al. 2004; Bruder, Sedoruk et al. 2008; Accorrtt, Stewart et al. 2011; Lin, Tsai et al. 2013) and the previously demonstrate clinical benefits of tDCS in the treatment of mood disorders (Berlim, Van den Eynde et al. 2013; Brunoni, Valiengo et al. 2013). Patients with MDD exhibit elevated oscillatory activity in the alpha band (8-12Hz), which is often localized to left frontal regions, resulting what has been called "frontal alpha asymmetry." (Leucher, Cook, et al. 2012; Henriques and Davidson 1990).

In this study, we will use more targeted stimulation waveforms by employing bilateral tACS instead of tDCS. We hypothesize that this choice of a more sophisticated waveform that directly enhances synchronization between the two hemispheres may be more effective in engaging the target. tDCS modulates overall activity levels of the targeted cortical area in a non-specific manner. Here, however, we propose to evaluate a more specific stimulation modality, tACS, (10 Hz stimulation frequency) that has been shown to selectively enhance cortical alpha rhythms (Neuling et al. 2013). Since the selected patient population reportedly exhibits specific deficits in the alpha frequency band, our stimulation approach will provide a more targeted and therefore possibly a more effective manipulation.

Mood ratings in this study will be obtained with the DRSP (Endicott et al. 2006). This rating scale is among the most widely used for assessment of symptoms of PMDD (and their requisite change in severity over the course of the menstrual cycle).

2 STUDY OBJECTIVES

The purpose of this study is to determine in women with PMDD whether a single session of tACS will alter left prefrontal alpha oscillatory power (enhance bifrontal symmetry, which is described as abnormal in PMDD). The secondary objective will be to determine if this ‘target engagement’ will differ by menstrual cycle phase. Our exploratory objective will be to examine whether changes in cortical dynamics will be associated with symptom reduction relative to baseline, pre-stimulation levels (obtained in the diagnostic feeder protocol IRB# 05-3000).

2.1 Primary Objective

- 2.1.1 To determine whether a single session of tACS in women with PMDD decreases left prefrontal alpha power, ascertained by comparing EEG prior and subsequent to tACS.
- 2.1.2 To determine whether a single session of tACS will alter prefrontal alpha symmetry

2.2 Secondary Objective

- 2.2.1 Determine whether the impact of tACS on left alpha power differs across menstrual cycle phases by comparing primary outcome measures obtained in the follicular vs the luteal phase of the menstrual cycle.

3 INVESTIGATIONAL PLAN

3.1 Study Design

Repeated measure, open-label study design.

Overview of study phases:

- **Screening/Baseline:** subjects will be followed for three months in a related protocol to document that subjects meet criteria for PMDD, showing affective symptoms of requisite severity as present during the luteal phase and relatively absent during the follicular phase.
- **Intervention/Treatment:** a single 40-minute session of tACS, administered once each in the follicular and luteal phases of the menstrual cycle

- **Follow up:** subjects will be followed with daily ratings until completion of the menstrual cycle following the second tACS. Any subject endorsing suicidal ideation, severe deterioration of mood, or distressing somatic symptoms on daily rating forms will be referred to [name] for acute evaluation and determination of appropriate subsequent clinical response.
- **Unscheduled Visits:** not applicable

3.2 Allocation to Treatment Groups and Blinding (if applicable): Not applicable

3.3 Study Duration, Enrollment and Number of Subjects

The study is anticipated to last five years. After being shown as eligible (in our screening protocol), subjects will sign an informed consent form and be deemed as enrolled when they have participated in the first tACS session. We will enroll 22 subjects to accommodate a 10% drop-out and achieve a sample size of 20. Each subject's participation is expected to last approximately one month. Two tACS sessions with pre-post EEG recordings will occur, one during the follicular phase (5-9 days after menstruation) and one in the luteal, premenstrual phase (9-13 days after ovulation). Subjects will test their urine at home each morning for approximately one week to determine ovulation. Each tACS/EEG session will last up to 90 minutes. There will be approximately 20 people in this research study.

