Subject Population	
Inclusion Criteria:
 
 Age 18-52

key criteria for Inclusion and Exclusion:	
 · Have a prospectively confirmed diagnosis of PMDD · Regularly menstruating without hormonal contraceptives · Medication free or regularly taking medication that has no effect on the nervous system · Not currently pregnant or planning to become pregnant 
Exclusion Criteria:
 
 · Brain surgery or brain implants, including cochlear implants or aneurysm clips · Neurologic disease (e.g. epilepsy or brain tumor) · Traumatic brain injury · Pregnant or nursing · An unstable medical illness (e.g. congestive heart failure or end-stage kidney disease) · History of severe or recurrent substance abuse within 2 years of study enrollment · History of suicidal behavior within 5 years of study enrollment · UNC Department of Psychiatry faculty, employee, or trainee
Number Of Subjects	20
Study Duration	
Each subject's participation is expected to last approximately one month. Two tACS with EEG recording sessions will occur, one during the follicular phase (5-9 days after menstruation) and one in the luteal, premenstrual phase (9-13 days after ovulation). Subjects will test their urine at home each morning for approximately one week to determine ovulation. Each tACS/EEG session will last up to 90 minutes.
 
The entire study is expected to last four and a half years

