4.1 Screening/Baseline Visit procedures

Effect of Menstrual Phase on Target Engagement

Diagnostic/Baseline Phase: We will attempt to recruit subjects whose PMDD status has been confirmed in our screening protocol (diagnostic study). Using the DRSP (Daily Record of Severity of Problems), subjects must show symptom severity of 4 or greater (scale range 1-6) for two days on a core emotional symptom in the luteal phase, absence of symptom severity during the follicular phase, and a 30% or greater increase in severity of symptoms in the 7 days preceding menses with 7 days following the end of menses. For those who meet criteria, we will describe the tACS study during their last visit in the diagnostic (screening) study. It will be during this in person visit that interested subjects would review the consent form and we would confirm eligibility for the tACS study. Consequently, no separate recruitment materials or phone screening materials are required for this study as all women will be recruited from the diagnostic study. After consent is provided, subjects will be asked to call and notify the study staff when they begin menstruating. If the subject is randomized to receive tACS in the follicular phase first, they will schedule a tACS session within 9 days of the onset of menses. If they are randomized to receive tACS in the luteal phase first, the subjects will then perform a home urine ovulation test every morning until they receive a positive result, at which point they can schedule their tACS session 9 - 13 days after the positive test result.

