6 STATISTICAL CONSIDERATION

This is repeated, single intervention (tACS) administered during the follicular and luteal phase. Change in left prefrontal alpha power on EEG is the primary outcomes. Effect of menstrual cycle phase is the secondary outcome. We plan to analyze our data using a repeated measure analysis of variance (ANOVA-R), with two within subject variables, each with two levels: time (pre vs post tACS), and menstrual cycle phase (follicular vs luteal). We will assess any effects of order of administration (follicular first vs luteal first) by including order as a between-subjects variable.

Clinical symptoms will be quantified as the mean of daily nighttime ratings (individual symptoms rated from 1 to 6) collected in the follicular (days 4 – 9) and luteal phases (the 6 days preceding menses) as recorded in the DRSP.

Decrease in left prefrontal power (reflection of reduction in alpha asymmetry) will be calculated by comparing results from the following time points: 1) immediately before the stimulation and 2) immediately following the stimulation in each of the follicular and luteal phases.

The main intent of this study is to conduct a pilot study, the results of which could be used in a larger trial that is appropriately powered for efficacy. Nonetheless, we intend to determine whether tACS influences alpha coherence on EEG. Due to the novelty of the application and the treatment strategy, we do not have all the required parameters to estimate the power for the repeated measure design on alpha coherence on EEG. However, the primary purpose is to demonstrate tACS associated changes in alpha coherence and whether that differs by cycle phase. The aim to demonstrate ‘target engagement’ does not necessarily lend itself to traditional power calculations and we will rely on [name] extensive experience with analyzing these data. In his experience, he is confident that if, in fact, if there are menstrual cycle differences in alpha coherence, 20 participants will be sufficient to demonstrate that effect.

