11 RECRUITMENT STRATEGY

Potential subjects will have already identified themselves by participating in our diagnostic study. Subjects who will enter the experiment will be those women who demonstrate the presence of PMDD, defined by the demonstration with daily mood ratings of a 30% or more increase in mean affective symptom ratings in the seven days prior to menses (luteal phase) compared with ratings during the seven days following the cessation of menses (follicular phase).

Based on when potential subjects are first identified as meeting criteria, they will either be recruited (and screened) at the second visit of the diagnostic feeder study, or they will be contacted by phone and re-screened via telephone interview. Given that the exclusion criteria for both the feeder study and this study are similar, the re-screening process is simply used to confirm that nothing has changed since they participated in the feeder study.

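### The follicular session window is stated in two conflicting ways, so sessions on different cycle days can all be labelled follicular in the secondary phase contrast

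*Combined protocol and SAP*

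**What the plan says.** The follicular session is timed by two rules.

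- **Duration rule** (synopsis, Study Duration; section 3.3): "one during the follicular phase (5-9 days after menstruation) and one in the luteal, premenstrual phase (9-13 days after ovulation"). Day zero of the follicular count is not stated.
- **Scheduling rule** (synopsis, Study Phases; section 4.1): "they will schedule a tACS session within 9 days of the onset of menses". It has an anchor and an upper limit but no lower limit. It is written only for women randomized to the follicular session first. For luteal-first women, the synopsis says only that the second session falls in the opposite phase.

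Two other follicular windows serve other purposes. Section 6 averages DRSP symptom ratings "collected in the follicular (days 4 – 9) and luteal phases (the 6 days preceding menses) as recorded in the DRSP". The diagnostic rule in section 11 compares premenstrual ratings with "ratings during the seven days following the cessation of menses (follicular phase").

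The luteal session is 9-13 days after ovulation in section 3.3, and "9 - 13 days after the positive test result" in section 4.1.

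Phase is the subject of objective 2.2.1 and of the secondary endpoint in 6.2. It is also one of the two within-subject factors in section 6.

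**The concern.** Staff who follow different sections could hold the follicular session on quite different cycle days, from the first days of bleeding to about mid-cycle, and every such session would enter the analysis as follicular. Each woman has one session per phase and about 20 women are planned, so a session at an unintended time is that woman's whole follicular observation.

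The background section ties PMDD symptoms to changes in gonadal hormones and says the alpha asymmetry worsens in the luteal but not the follicular phase. On the protocol's own reasoning, timing defines the exposure being compared.

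Order adds to this. The scheduling rule is written only for follicular-first women, so the only numeric follicular window that covers luteal-first women is the duration rule. If each text is followed as written, cycle day could differ by order group, and an apparent order effect could partly be a cycle-day effect. Sections 6 and 6.3 both assess order as a between-subjects variable.

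**Working it through.** The documents give no figure to reproduce, so the check maps both rules to cycle days and intersects them.

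**Inputs.** Day 1 is the onset of menses. The duration rule is 5-9 days after menstruation (3.3). The scheduling rule is up to 9 days from onset (4.1): days 1-9 if onset counts as the first day, or days 1-10 if onset counts as zero. Bleed length L is not in the documents; I assume 2 to 8 days.

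**Reading 1: the duration rule counts from the end of bleeding.** It then covers days L+5 to L+9.

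| L (assumed) | Duration rule | Shared with days 1-9 | Shared with days 1-10 |
|---|---|---|---|
| 2 | 7-11 | 7-9 | 7-10 |
| 3 | 8-12 | 8-9 | 8-10 |
| 4 | 9-13 | 9 | 9-10 |
| 5 | 10-14 | none | 10 |
| 6 | 11-15 | none | none |
| 7 | 12-16 | none | none |
| 8 | 13-17 | none | none |

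The two rules stop overlapping at 5 or 6 days of bleeding, depending on the day count.

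**Reading 2: the duration rule counts from onset.** It covers days 5-9 and lies wholly inside days 1-9. The scheduling rule still admits days 1-4, which the duration rule excludes. With onset as day zero, the duration rule is days 6-10 and the extra days are 1-5.

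Under both readings the scheduling rule admits early bleeding days that the duration rule does not.

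**Illustration of dilution.** Suppose a share p of follicular sessions falls on days that carry a fraction f of the intended phase difference. The contrast is then multiplied by 1 − p(1 − f), and the effective number of women by the square of that factor. Neither p nor f is in the documents.

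- p = 0 (all sessions on days 5-9, which meet both rules under reading 2): factor 1, no loss.
- p = 3/9 (sessions spread evenly over days 1-9, with days 1-3 off target), f = 0.5: 1 − 1/6 = 0.83; 0.83² = 0.69; 20 × 0.69 ≈ 14 women.
- p = 3/9, f = 0: 1 − 1/3 = 0.67; 0.67² = 0.44; 20 × 0.44 ≈ 9 women.

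Taking days 1-3 as off target borrows the days 4-9 window from the DRSP averaging rule, which is not a session window. The cases only show a span.

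**The case against.** The best defence is that the two rules are compatible. Where the plan means the end of bleeding it says so, as in the diagnostic criteria in 3.4, 4.1, 5 and 11; the duration rule does not. The scheduling text is anchored to onset, and both rules share the upper limit of 9. Read from onset, a session on days 5-9 satisfies both. This stands as far as it goes: complete non-overlap is one possible reading and is not established. It does not remove the conflict, because the scheduling rule has no lower limit and the duration rule has no stated day zero.

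Four stronger readings are tempting, and the documents do not support them.

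- **The luteal window is ambiguous too.** It is not. Section 3.3 says the urine test is used to determine ovulation, and the interval is 9-13 days in every place.
- **The session windows contradict days 4-9 or the seven days after menses.** Those define symptom averaging and diagnosis. Neither has to equal a session window, and the mood analysis in 6.3 uses luteal means only.
- **The study is worth only about 9 women for the phase contrast.** That is the extreme case above and needs both an even spread of sessions and no phase difference on days 1-3. Women report onset before they schedule, which makes an even spread from day 1 doubtful.
- **Section 4.1 is what staff will follow.** No section is given precedence.

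It is also fair to say that this is a self-described pilot, and that the primary outcome is a change within each session.

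**Conclusion.** The concern holds for the follicular session window. The current text gives two different rules and does not reconcile them. Under either reading of the duration rule, the scheduling rule admits days that the other excludes. If the count starts at the end of bleeding, the rules share no day once bleeding lasts about 5-6 days; that threshold rests on assumed bleed lengths and on how days are counted.

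The consequence is a possible blurring of the secondary phase contrast, and possibly a cycle-day difference between order groups. Its size cannot be derived from the documents. The primary pre-post comparison is made within each session and is little affected. This should be fixed, but it does not undermine the primary analysis, and a reader should not infer that the phase comparison as a whole is undefined: the luteal side is consistent.

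**What to change.** 1. Reconcile the two synopsis rows (Study Duration, Study Phases) and sections 3.3 and 4.1 to one follicular session window. State its day zero, lower limit and upper limit, and apply it to both order groups. The choice of window belongs to the clinical team.
2. Record cycle day at every session, and days from the positive ovulation test where available. For a follicular-first session that test comes later in the cycle, so the value can only be added afterwards. If the chosen anchor is the end of bleeding, record that date as well.
3. Keep all sessions in the main phase contrast. Excluding out-of-window sessions there would break within-woman pairs in a study of 20. Add a sensitivity analysis limited to sessions inside the reconciled window.

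The cost is a wording change and one or two dates per session. Section 4.1 already has women report menses onset and test for ovulation. The small downside is tighter scheduling for some women.

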3.4 Study Population

-Inclusion and Exclusion Criteria

Subjects will be women with PMDD. All subjects will have had their diagnoses confirmed by participation in our diagnostic study. The diagnosis requires demonstration of at least a 30% increase in symptom ratings in the seven days preceding menses compared with the seven days following the cessation of menses in two of three menstrual cycles.

In addition to PMDD diagnosis, all women enrolled must also meet the following criteria:

Inclusion Criteria:

- Age 18-52
- Have participated in our PMDD diagnostic study
- Regularly menstruating without hormonal contraceptives (e.g., birth control pills, injections, implants, progestin IUDs)
- Medication free or regularly taking medication that has no effect on the nervous system
- Not currently pregnant or planning to become pregnant
- With sufficient resource to prevent pregnancy

Exclusion Criteria:

- Brain surgery or brain implants (e.g., cochlear implants or aneurysm clips)
- Neurologic disease (e.g., epilepsy or a brain tumor)
- Traumatic brain injury
- Pregnant or nursing
- Any unstable medical illness (e.g., congestive heart failure or end-stage kidney disease)
- History of severe or recurrent substance use disorder, or any substance abuse within 2 years of study enrollment
- History of suicidal behavior within 5 years of study enrollment
- UNC Psychiatry faculty, employee, or trainee
-

4 STUDY PROCEDURES

- tACS administered on two
- High density EEG recording before and after each tACS administration
- Daily Record of Severity of Problems (DRSP) ratings daily throughout the study administered electronically via Qualtrics survey platform. This 20-item self-report rating scale assesses physical and mood symptoms that accompany ovarian hormone changes and is often used as a dimensional measure of PMDD.

4.1 Screening/Baseline Visit procedures

Effect of Menstrual Phase on Target Engagement

Diagnostic/Baseline Phase: We will attempt to recruit subjects whose PMDD status has been confirmed in our screening protocol (diagnostic study). Using the DRSP (Daily Record of Severity of Problems), subjects must show symptom severity of 4 or greater (scale range 1-6) for two days on a core emotional symptom in the luteal phase, absence of symptom severity during the follicular phase, and a 30% or greater increase in severity of symptoms in the 7 days preceding menses with 7 days following the end of menses. For those who meet criteria, we will describe the tACS study during their last visit in the diagnostic (screening) study. It will be during this in person visit that interested subjects would review the consent form and we would confirm eligibility for the tACS study. Consequently, no separate recruitment materials or phone screening materials are required for this study as all women will be recruited from the diagnostic study. After consent is provided, subjects will be asked to call and notify the study staff when they begin menstruating. If the subject is randomized to receive tACS in the follicular phase first, they will schedule a tACS session within 9 days of the onset of menses. If they are randomized to receive tACS in the luteal phase first, the subjects will then perform a home urine ovulation test every morning until they receive a positive result, at which point they can schedule their tACS session 9 - 13 days after the positive test result.

Transcranial Current Stimulation: Subjects will report for bilateral stimulation with tACS (one session) per menstrual phase, over the course of one menstrual cycle (unless it is an anovulatory cycle, in which case the participant will be asked to conduct the ovulation testing for one additional cycle). Each participant will receive tACS once in the follicular cycle phase and once in the luteal cycle phase, in counterbalanced order. The tACS stimulation will deliver a maximum amplitude of 2mA for a total of 40 minutes of stimulation per session. Electrodes will be saline soaked, 5x5cm, and placed over F3 and F4 locations to target dorsolateral prefrontal cortex. The return electrode will be located over CZ. A transcranial current stimulator designed by the [name] lab (XCSITE 100 stimulator) will be used. After the first tACS session, participants will be instructed to begin daily mood ratings as recorded in the Daily Record of Severity of Problems. This 20-item self-report rating scale assesses physical and mood symptoms that accompany ovarian hormone changes and is often used as a dimensional measure of PMDD.

Electroencephalography (EEG): Each EEG session will last 8 minutes, and participants will alternate between having eyes open and closed at 2-minute intervals. A total of four EEG recordings will be performed throughout participation; two recordings per menstrual phase to be collected before and after stimulation. EEG will be recorded with a standard Nicolet v32

clinical EEG machine that is approved for clinical use and that has been used in all previous studies by the [name] Lab. Briefly, 10mm gold cup electrodes are fitted to the individual participants for brief, non-invasive recordings of brain activity.

